# Epistemological position

This work is pragmatic and contextual: the claims to produce evidence turn on the plausible utility within the contexts of evidence of clinical psychology, psychiatry and psychotherapy.

# General statistical approach

This is a quantitative programme of Practice Based Evidence (PBE, e.g. Margison et al., 2000) work largely in the spirit of "realist evaluation" (e.g. Van Belle et al., 2016)and not an Evidence Based Practice (EBP) Randomised Controlled Trial (RCT). The design is a cohort follow-up study and the naturalistic data collection means that the statistical methods are exploratory and descriptive even where null hypothesis testing will be used. There is no randomisation or experimental control meaning that there will always be multiple ways of explaining associations and the design is not focused as in an RCT on a single primary contrast of interest and a small set of secondary tests. The terminology of sample and population will be used and estimation methods (implicitly of population parameters) will be central, and population hypothesis tests used where useful and meaningful. As participation was voluntary the data are inevitably, ethically, incomplete and not a true, complete census,

### 1. Multiple tests and p-value hunting/hacking

We recognise that there are no perfect ways of exploring such data. There are many areas where exploration of associations, e.g. between plausible predictor and response variables can usefully be informed by null hypothesis testing. As there are many such associations, this raises the classical "multiple tests" issue: that if all the null hypotheses about the population were true (and independent) then the expectation of a single test being "significant" at the alpha level (.05) rises rapidly, and markedly above .05, as the number of tests rises. This issue has of course been know from the invention of hypothesis testing, for a readable early discussion in relation to mental health research see (e.g. Grove & Andreason, 1982). This leads to two related issues: the simple one of the elevated "studywise" false positive rate, and the issue of "p-value hunting/hacking" (touched on as part of the recent resurgence of interest in trying to reduce the dangers of naïve use of hypothesis testing, e.g. (Amrhein et al., 2019; APA, 2016; Wasserstein & Lazar, 2016).

There is an extensive literature with arguments for and against application of methods to reduce the overall "studywise" false positive rate to .05, and various methods by which to do this (Primo de Carvalho Alves & Sica da Rocha, 2019 e.g.). Given the diversity of areas in which we will be exploring associations and where null hypothesis significance testing (NHST) has some value as a decision rule, we do not propose to use any of the methods of controlling for the inevitably elevated false positive rate. However, we do propose to be consistent and clear in recognising the risk. All hypothesis tests will be reported with the actual p value, not as "p < .05" versus "NS" (or some other ordinal categorisation of p values by asterixes). Where possible, 95% confidence intervals (CIs) will be reported for all statistics. To be precise, we will report the Bias Corrected Adjusted, (bca) 95% CI from 1000 bootstrap replications unless it is not available in which case the percential CI will be used, see (Carpenter & Bithell, 2000; Puth et al., 2015).

That issue of the inflated type I error rate that is bound to arise from there being multiple questions of interest leads to the option for deliberate or uninformed "p-value

© CE & CP for ITAMITED group

Page 2 of 14

hunting/hacking" with the considerable risk of severely misleading findings. We recognise the multiple tests issue and wish to conduct analyses as likely to result in replicable findings as possible. We also see the only protection against the accusation of p-value hunting/hacking is to be as clear as possible about the distinction between planned, i.e. a priori analyses, and "emergent" ones, i.e. those conducted in exploration of, and intended to throw more light on unexpected findings. With a very complex clinical service, multiple important aims and an extensive dataset, there are an almost infinite number of possible analyses and a very large number of important analyses apparent *a priori*. This makes it challenging even to summarise the planned analyses; hence the length of this, Data Analysis Plan (DAP) which is itself a shortened "freeze" of a much larger document. This document is being submitted with the study protocol paper and designed to complement that and enable a moderately thorough coverage of the *a priori* analyses and the methodological/statistical issues that would otherwise overwhelm the paper. In line with our epistemological position, this document has been written trying to be readable to research interested clinicians as well as clinical researchers, the target context for findings, not for statisticians and many technical statistical issues are presented as simply as possible.

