- Construct validity in terms of factor analyses within and across measures. We 0 believe that factor analytic methods are often overvalued when applied to short, broad coverage measures of diverse problems, measures designed as much to be good within-individual reflections of change as to be good between-individual comparators. However, both in clinical practice and research all the self-report measures used in the study are used both for comparisons across individuals and to measure change over time hence it is important, as with reporting the internal reliability, to explore factor structure. The within measure exploration will use confirmatory factor analysis (CFA) where either there are widely used scale scores for the measure or where there has been debate in the literature about whether a measure (or scale/score) is unidimesional or has more factors of interpersonal difference. As the indicators (items) are short ordinal scales and as the latent variables are almost certainly not Gaussian in distribution, we will use both maximum likelihood (ML) and diagonally weighted least squares (DWLS) (Li, 2016; Rhemtulla et al., 2012) estimation and appropriate scaled/robust fit

statistics (Satorra & Bentler, 2010) for the estimation method. Assuming the DWLS and robust fit statistics give better fit these will be reported with a note about the ML fit. If numbers allow (n > 250) separate analyses will be conducted by gender, age and diagnosis.

We will explore factorial measurement invariance across first and second completions (exempting items clearly impacted by the restrictions of hospitalisation). We will also explore invariance between groups by gender, sensible age groups (determined partly by cell sizes, here again n > 250) and diagnoses (again, restricted by sufficient cell sizes). For both temporal and between group analyses we expect only quite low levels of invariance as we believe there are very real changes and differences in structure, hence the focus will be more on the magnitude of the impacts on scores of the invariance rather than whether statistically significant invariance is or is not present. If fit to the scale design is particularly bad, exploratory factor analyses will be conducted and reported.

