As well as within-measure analyses, we will also conduct across-measure factor analyses as these allow construct validity to check on where one might expect shared factor structure (i.e. for (Ch)EAT and BITE) or might expect largely unrelated factor structure (i.e. between (YP-)CORE and both (Ch)EAT and BITE). These analyses will be CFA by design structure and EFA if fit to design structure is clearly very poor.

- If some measures/scores show clear fit to unidimensionality, we will conduct Item Response Theory (IRT) analyses to identify cutting points and potential evidence that the conventional scoring of the measures may be suboptimal for cross-sectional comparisons.
- Convergent validity between related measures (EAT-26/CHEAT-26 and BITE) and convergent and divergent validity between them and diagnoses and BMI. These are more conventional explorations than the item level across-measure factor analyses noted above. We will explore scatterplots for marked non-linearity or

clearly non-zero intercepts and, assuming there are not major issues of those kinds, will report Spearman rho and Pearson R correlations with bootstrap confidence intervals. Reporting both correlations maximises comparability with existing literature as Spearman correlations have often been reported in the past, before the widespread availability of bootstrapping, as score distributions are generally not Gaussian. If numbers allow (n > 80) separate analyses will be conducted by gender, age and diagnosis.

Divergent validity/confounding against gender, age, first language, education.
 Distributions will be compared by groups (with sensible age groups) and the simple scattergrams against age inspected. Unless clearly inappropriate Pearson correlations with age, and mean differences by groups, will be reported with bootstrapped CIs.

To explore the psychometrics of change (tranche  $\underline{2}$  and  $\underline{3}$ ):

- Where participants have sufficient completed measures (n > 20) we will to apply P-technique estimation of Cronbach's alpha within individuals, within and across measures. For the small number of participants with the larger number of sufficient completions (n > 40) we will also explore P-technique "factor" structure (actually Principal Component Analyses (PCA)) to show the structures that emerge where the sequences of completed measures within individuals allow this.

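### The bootstrap rule for all statistics needs an exemption for CFA fit indices: ordinary resampling gives RMSEA and CFI intervals with far too little coverage, which usually miss their own estimate when the model is correct

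*SAP*

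**What the plan says.** The general rule is in the SAP, General statistical approach, section 1 (multiple tests): "Where possible, 95% confidence intervals (CIs) will be reported for all statistics". The next sentence fixes the method as the "Bias Corrected Adjusted, (bca) 95% CI from 1000 bootstrap replications unless it is not available in which case the percential CI will be used". The rule exempts no class of statistic.

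Secondary objective 2 (psychometric properties) plans CFA by ML and DWLS "estimation and appropriate scaled/robust fit" statistics. On what is reported it says: "Assuming the DWLS and robust fit statistics give better fit these will be reported with a note about the ML fit". Separate CFAs by gender, age and diagnosis are planned where n > 250. This section mentions no interval for fit and no other way to obtain one.

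Two later steps depend on fit: "If fit to the scale design is particularly bad, exploratory factor analyses will be conducted and reported", and "If some measures/scores show clear fit to unidimensionality, we will conduct Item Response Theory (IRT) analyses". Neither names an index, a cut-off or an interval.

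**The concern.** Bootstrapping suits means, effect sizes, correlations and reliability coefficients. It does not suit a statistic that measures how far the data lie from a fitted model. A resample is drawn from the observed sample, which already departs from the model by chance. Resampling treats that chance departure as real and adds a second round of sampling error. Nearly every replicate then fits worse than the sample did.

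This damages both branches of the rule. BCa needs the share of replicates below the estimate to compute its bias correction. If that share is zero, the correction is infinite and BCa is undefined; if it is very small, the limits collapse onto the most extreme replicates. The fallback, "unless it is not available in which case the percential CI will be used", then takes its limits from the shifted distribution itself.

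At stake is the credibility of the psychometric tables. Fit would carry an interval labelled 95% that has far lower coverage and often does not contain the number beside it. Readers judging scale structure without a stated cut-off would have that interval in front of them.

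**Working it through.** The SAP gives no fit value, sample size or power figure, so there is nothing of its own to reproduce.

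**Inputs from the SAP.** The interval rule and its 1000 replications; ML and DWLS estimation; the n > 250 threshold for subgroup CFA; 26 items, taken from the name EAT-26.

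**Assumptions.** Simulated normal items with loadings 0.6 (0.7 where stated); one factor for 10 items; three factors for 26 items; n = 250 and 1000. The total sample size is not in the SAP.

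**Degrees of freedom.** 10 items, one factor: 55 variances and covariances − 20 parameters = 35. 26 items, three factors: 351 − (26 + 26 + 3) = 296.

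**Theory.** RMSEA = √[max(0, T − df) / (df(n − 1))]. If the model is true, T averages about df. Under case resampling T* is roughly noncentral chi-square with mean T + df, hence about 2 df. Substituting gives

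RMSEA* ≈ √[RMSEA² + 1/(n − 1)].

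With true RMSEA 0:
- n = 250: √(1/249) = 0.063
- n = 1000: √(1/999) = 0.032

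With true RMSEA 0.042:
- n = 250: √(0.00176 + 0.00402) = 0.076
- n = 1000: √(0.00176 + 0.00100) = 0.053

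The simulated bootstrap medians for 10 items were 0.063, 0.031, 0.075 and 0.052 in the same order, so the formula describes the shift well.

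**Simulation of the planned rule, model exactly true.** ML, 1000 replications, BCa with jackknife acceleration, percentile if BCa was undefined. The last row is percentile only.

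| Items, n | Data sets | RMSEA interval covers 0 | contains own estimate | CFI interval covers 1 | contains own estimate |
|---|---|---|---|---|---|
| 10, 250 | 100 | 21% | 6% | 37% | 19% |
| 10, 1000 | 40 | 25% | 3% | 35% | 10% |
| 26, 250 | 15 | 0% | 0% | 0% | 0% |
| 26, 1000 | 8 | 0% | 0% | 0% | 0% |

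- **26 items, n = 250.** BCa was never available. The mean RMSEA estimate was 0.009, with percentile interval 0.055 to 0.075; the mean CFI estimate was 0.994, with interval 0.80 to 0.90. The chi-square scale agrees: the mean limits for T* were 516.9 and 715.7, and √[(516.9 − 296)/(296 × 249)] = 0.055, √[(715.7 − 296)/(296 × 249)] = 0.075. Zero of 15 is compatible with a true coverage of at most 1 − 0.025^(1/15) = 22%.
- **26 items, n = 1000.** RMSEA interval 0.027 to 0.036, CFI 0.946 to 0.970: still wrong, but not a picture of bad fit.
- **10 items, n = 250.** BCa was available for RMSEA in 45% of data sets and for CFI in 58%. Where available, the mean limits were 0.011 to 0.016 for RMSEA (width about 0.004) and 0.995 to 0.997 for CFI. These contained their own estimate in 0% and 22%. The error here is false precision, not a shift to misfit.

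**Modest true misfit.** 10 items, loadings 0.7, true RMSEA 0.042, percentile interval only, 500 replications, 60 data sets per cell. At n = 250 the interval covered the truth in 33% and held the estimate in 7%. At n = 1000 the figures were 63% and 83%, with mean interval 0.041 to 0.064.

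**DWLS.** One factor, 10 binary items, loadings 0.7, tetrachoric DWLS with mean-scaled chi-square, n = 250, 80 data sets, 300 replicates. Chi-square/df averaged 0.99 observed and 2.02 in the bootstrap. The mean RMSEA estimate was 0.011 and the mean percentile interval 0.030 to 0.089, which held the true 0 in 5% and its own estimate in 6%. The mechanism carries over to the estimator the plan expects to report.

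**Alternative.** In a separate ML run at n = 250 with a correct one-factor model, the noncentral chi-square interval for RMSEA contained the true 0 in 87% of 60 data sets (10 items) and in all of 16 (26 items). That is imperfect on so few data sets, but of a different order from the bootstrap.

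**The case against.** **The plan never says that fit will be bootstrapped.** The rule stands in a section about p-values and opens with a qualifier. The CFA text speaks of scaled and robust statistics, and bootstrap intervals are named again where they are clearly meant: mean change, effect sizes, correlations and group differences. A sensible analyst might never bootstrap RMSEA. This is a fair reading of intent, and part of it stands: the defect depends on taking the rule at its word. But the qualifier does not exclude fit, because a percentile interval for RMSEA can always be computed, and the CFA text offers no other interval. A rule meant to be precise should not depend on the analyst knowing when to ignore it.

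**No decision hangs on the interval.** This stands. A reader might infer that correct scales will be sent to exploratory factor analysis or denied IRT because of these intervals. The SAP does not support that. Its triggers name no interval, the point estimates are still reported, and in the simulations they correctly show good fit. An interval lying wholly above its own estimate would also be noticed.

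**The direction and size are not uniform.** This stands too. A reader might infer that well-fitting scales will always look badly fitting. Short scales with a computable BCa interval show the opposite appearance, n = 1000 leaves values that look acceptable, and real misfit restores some coverage. The n > 250 threshold applies to subgroup CFA only.

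**The simulated conditions are not the study's.** Most runs used normal items and ML, while the plan has short ordinal items and expects DWLS. The binary-item DWLS run narrows this gap for the percentile interval, but items with more categories were not tried.

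**Conclusion.** The point holds in a limited form. Read as written, the rule assigns CFA fit indices an interval that is invalid for them. With a correct model, simulated coverage of the planned interval was 0% to 37% instead of 95%, and it contained its own estimate in at most 19% of data sets. The mildest case tried, percentile intervals with true RMSEA 0.042 at n = 1000, reached 63% coverage. Long scales near n = 250 are worst, and there the interval is shifted toward misfit.

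Well-fitting scales can therefore look badly fitting, but it does not follow that they will. The conclusion rests on a literal reading of the rule, on assumed loadings and factor structures, and on few data sets in the 26-item cells. SRMR is left out because it is positive in any sample, so exclusion of 0 tells nothing. The matter concerns a secondary, descriptive objective and does not touch the primary effectiveness analyses. It should be corrected, but it does not threaten the study.

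**What to change.** In section 1 of the General statistical approach, add one sentence exempting model-fit statistics from the bootstrap rule. RMSEA is reported with a 95% noncentral chi-square interval based on the scaled or robust statistic, and CFI and other indices as point estimates. If a bootstrap test of fit is wanted, it should resample data transformed to satisfy the fitted model (Bollen-Stine). BCa stays for means, effect sizes, correlations and reliability coefficients.

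The cost is that sentence. The analytic RMSEA interval is standard software output, and no other analysis in the plan changes.

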# 3. Primary objective: Effectiveness of ITAMITED as it is applied routinely in its natural context.

We will analyse effectiveness with three complementary analyses performed for data/analysis tranches 2 and 3.

(a) Baseline/termination change. This is has been the traditional focus of many existing explorations of effectiveness of treatment. We will report both mean change and also effect sizes reporting Cohen's d2 and dz (Cohen, 1988) (the ratio of mean change to baseline SD and the ratio of mean change to SD of change respectively) and report these with bootstrap CIs. As well as reporting the global aggregate mean shifts with bootstrap 95% CI for each score. We will report the regression of termination scores on baseline scores and the distributions of change scores.

We will explore the impact of baseline variables: gender, age, diagnosis, demographic

variables, medication use and service on change. These predictor effects will be explored entering them as predictors of termination scores/values in ANOVA models with attention paid to the almost certain violation of assumptions of the ANOVA and exploration of mitigation of those violations. As gender and age are such crucial variables in Eating Disorders (Eds) the effects of entering these as predictors (or analysing separately be gender) on effects of other variables will be reported.

To address individual change we will report the Jacobson plot of termination against baseline scores for all scores and report the RCSC breakdown of change on each measure where it is possible to define the CSC and RCI.

(b) Multilevel models (MLM) of rates of change. MLM allows analysis of change slopes across diverse durations of therapy/ascertainment and the method handles the nonindependence of observations arising from the repeated measures within participant appropriately. These analyses can give a much more nuanced picture of change than baseline/termination analyses while allowing exploration of the effects of the same predictors and covariates analysed in (a). As for (a), durations of therapy are not directly reflected in the analyses though in contrast to (a), all data across all durations of data collection are used rather than just the first and last values.

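### Setting 1000 replications for the BCa intervals leaves avoidable random error in the limits; 10,000 would cut it by about two thirds for statistics that are quick to compute.

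*SAP*

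**What the plan says.** The setting is in the SAP, General statistical approach, section 1 (Multiple tests and p-value hunting/hacking). "Where possible, 95% confidence intervals (CIs) will be reported for all statistics", and the type is then made specific: BCa, "95% CI from 1000 bootstrap replications unless it is not available", with the percentile interval as fallback. No reason is given for 1000.

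The intervals are used in at least two places:

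- Section 3 (Primary objective), part (a): for d2 and dz the plan is to "report these with bootstrap CIs". Mean change on each score also gets a bootstrap 95% CI.
- Secondary objective 2 (psychometric properties): Spearman and Pearson correlations and group mean differences get bootstrap CIs. For the convergent validity correlations, "If numbers allow (n > 80) separate analyses will be conducted by gender, age and diagnosis".

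The General statistical approach also says that "the statistical methods are exploratory and descriptive even where null hypothesis testing will be used".

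**The concern.** At 1000 replications a 95% limit sits where only about 0.025 × 1000 = 25 replicates lie beyond it. BCa adds a second source of noise. Its bias correction is estimated from the same replicates, so the level at which the quantile is read also varies from run to run. BCa limits are therefore noisier than percentile limits from the same number of replications.

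The same data analysed with another seed will give somewhat different limits. In the smaller groups the second decimal of an effect size can change, and an interval that ends close to the null may include it on one run and exclude it on the next. Sampling error cannot be reduced once the data are in, but this error can.

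**Working it through.** The SAP derives no figure here that could be reproduced; 1000 is a setting. The check asks how much random error it leaves.

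**Inputs from the SAP:** BCa 95% interval and B = 1000 (General statistical approach, section 1); dz as mean change over the SD of change (section 3, part (a)); n = 80, the threshold for separate correlation analyses; n = 250, the threshold for separate factor analyses, used here only as a middle size.

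**Assumptions:** true dz = 0.5; n = 1000 as a large case, since the SAP gives no total sample size; normally distributed change scores.

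**Step 1. Percentile limit.** In units of the statistic's standard error (SE), the Monte Carlo SD of a limit is sqrt(p(1 − p)/B)/φ(z_p), with p = 0.025 and φ(1.96) = 0.0584.

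- B = 1000: sqrt(0.025 × 0.975/1000)/0.0584 = 0.0845 SE (simulated: 0.0842)
- B = 10,000: 0.0267 SE

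**Step 2. BCa limit.** Simulated from a normal bootstrap distribution with acceleration 0, re-estimating the bias correction in each run (4000 runs at B = 1000, 1500 at B = 10,000).

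- B = 1000: about 0.106 SE, and 0.106/1.96 = 5.4% of the half-width
- B = 10,000: about 0.033 SE, and 0.033/1.96 = 1.7% of the half-width
- Expected reduction: 1 − 1/sqrt(10) = 68%

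**Step 3. Full BCa for dz**, with jackknife acceleration, on one fixed simulated sample per n (150 reruns per cell; 40 for n = 1000 at B = 10,000). Ranges cover the lower and upper limits.

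| n | B | SD of a limit (dz scale) | % of half-width | Seconds per interval |
|---|---|---|---|---|
| 80 | 1000 | 0.0107-0.0111 | 5.1-5.3 | 0.0011 |
| 80 | 10,000 | 0.0036-0.0040 | 1.7-1.9 | 0.0098 |
| 250 | 1000 | 0.0070 | 5.5-5.6 | 0.0024 |
| 250 | 10,000 | 0.0022-0.0023 | 1.7-1.8 | 0.0275 |
| 1000 | 1000 | 0.0035-0.0036 | 5.3-5.4 | 0.0104 |
| 1000 | 10,000 | 0.0008-0.0011 | 1.2-1.7 | 0.108 |

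Example for n = 80, B = 1000: the mean limits are 0.3238 and 0.7422, the half-width is 0.4184/2 = 0.2092, and 0.0107/0.2092 = 5.1%. A separate run with skewed data at n = 80 and 250 gave 5.2-5.7% at 1000 and 1.5-1.9% at 10,000.

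**Step 4. How often two seeds disagree about the null.** For a limit with Monte Carlo SD s (in SE), the mean absolute difference between two reruns is 1.13 s. Multiplying by the density of the estimate at the point where the interval just touches the null gives the chance of disagreement.

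- True null, two tails: 2 × 0.058 × 0.106 × 1.13 = 1.4% at 1000; with 0.033, 0.4% at 10,000
- True effect of 1.96 SE: 0.399 × 0.106 × 1.13 = 4.8% at 1000; with 0.033, 1.5% at 10,000

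**Step 5. Harm to the interval as such.** Under the ideal bootstrap distribution, mean coverage is 0.948 at 1000 (95% of runs 0.933 to 0.961) and 0.950 at 10,000 (0.945 to 0.954). Beside sampling error, the SD of a limit rises by sqrt(1 + 0.106²) − 1 = 0.6% at 1000.

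**The case against.** The strongest reply is that nothing here is wrong. The number is stated openly and in advance. Coverage hardly moves, and 0.6% on top of sampling error is negligible. The plan calls itself exploratory, reports actual p values and rejects a split into significant and not significant. It grants hypothesis tests some value as a decision rule but ties no rule to where a bootstrap limit falls. All of this stands, and it keeps the point minor. It does not show that the error is worth keeping where it can be reduced for a fraction of a second per interval.

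A reader might also infer more than the documents support:

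- *That 10,000 replications remove the error.* They leave about 1.7% of the half-width, and at n = 80 the second decimal of dz can still change.
- *That the change costs nothing.* It is ten times the computation. The timings are for dz alone. The plan also has multilevel, latent profile and factor models, and nothing shows that ten times the work is trivial for any of these that are bootstrapped.
- *That every reported limit is visibly affected.* Intervals are promised only where possible, and some will be percentile intervals with a smaller error (0.0845 against 0.106 SE). Visibility also depends on sample size, scale and rounding, and the SAP fixes neither a total sample size nor a rounding rule.
- *That the setting defeats the plan's aim of replicable findings.* In its context that aim concerns multiple testing and the separation of planned from emergent analyses, not reruns of the same data.

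That no seed is mentioned is not a fault in itself: the SAP describes itself as shortened from a much larger document, and seeds are normally fixed in code.

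**Conclusion.** The point holds as a minor, optional improvement. With 1000 replications, the seed-to-seed SD of a BCa limit is about 5-6% of the half-width, and 10,000 would bring it under 2%. In relative terms this barely depends on n. On the dz scale it is about 0.01 at n = 80, 0.007 at n = 250 and 0.0036 at n = 1000. Two runs on the same data would disagree about the null in roughly 1.4% of intervals under a true null and 4.8% for an effect of 1.96 SE.

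The intervals at 1000 remain valid and usable, and the SAP does not contradict itself. The absolute figures rest on an assumed dz of 0.5 and on assumed sample sizes. The disagreement rates rest on a normal approximation and on reading each interval against the null, which the plan does not require.

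**What to change.** In General statistical approach, section 1, replace the single figure of 1000 by a two-part rule:

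- For statistics that are quick to compute (mean change, d2, dz, correlations, group mean differences): BCa 95% intervals from at least 10,000 replications, with the seed recorded.
- For slow models, such as multilevel or factor models: a smaller number if needed, stated beside the interval.

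The percentile fallback can stay as it is. The recorded seed makes a rerun return the same limits; only the larger number reduces the error in them.

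The cost is one changed sentence and about ten times the bootstrap computing time, measured for dz at 0.01 s per interval at n = 80 and 0.11 s at n = 1000. No data collection or analysis method changes.
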